#### 5.2 Secondary Endpoint

Preliminary impact on adherence as assessed by tenofovir hair levels (long-term adherence): Change in tenofovir levels in hair from baseline and after 3 months of follow-up will be compared between the intervention and standard of care arm.

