STUDY DESIGN	This is a randomized, unblinded, open-label pilot study

PRIMARY OBJECTIVE	To test the acceptability to participants and impact on a longer-term metric of adherence among participants (assessed via tenofovir levels in hair) of implementing POC urine tenofovir testing and providing adherence feedback and motivational interview-based counseling among YMSM in the U.S.
NUMBER OF SUBJECTS	60 participants, 40 in the intervention arm and 20 in the standard-of-care arm
SUBJECT SELECTION CRITERIA	
Inclusion Criteria:
 
 
1. Age 18-30 years.
 
2. Primary sexual partners are male sex at birth
 
3. Able to understand, read, and speak English.
 
4. Currently taking TDF/FTC-based, daily PrEP and planning to continue for at least 3 months
 
5. Willing to provide a hair sample
 
 
Exclusion Criteria:
 
 
1. Any health condition that may interfere with participation or the ability to provide informed consent, including any debilitating or life-threatening conditions
 
2. Currently enrolled in another HIV intervention study.
 
3. Known to be HIV-infected.
 

POC TESTING	Urine tenofovir testing by lateral flow assay performed at each of 2 counseling sessions approximately 2-3 months apart
CONTROL	Participants will continue to receive standard of care at their PrEP clinic without the PrEP2-BAY adherence counseling intervention
DURATION OF SUBJECT PARTICIPATION AND DURATION OF STUDY	Participants will be enrolled in the study for a maximum of 3 months, including the enrollment period and 3 months of study follow-up.
PRIMARY ENDPOINT	
 
• Acceptability: Number of participants indicating satisfied or very satisfied with the intervention
 
• Description: Number of participants reporting to be "satisfied" or "very satisfied" about their overall experience on a five-point Likert scale.
 
• Time Frame: 3 months
 

SECONDARY ENDPOINTS	
 
• Change in tenofovir levels in hair from baseline and after 3 months of follow-up
 

PLANNED INTERIM ANALYSES	When approximately 50% of patients have completed all study procedures, an interim analysis of all data will be conducted by an

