	independent DSMB. Serious adverse events will be monitored by the committee on an ongoing basis throughout the study.
STATISTICS Primary Analysis Plan	
Acceptability will be the primary outcome for this pilot randomized controlled trial, and will be assessed via tabulation of survey results with graded answers in the intervention arm. Frequency distributions of the Likert scale will be summarized. Advantages and disadvantages of the bioassay enhanced brief adherence intervention will be tabulated, including manually reviewing and assigning open-ended responses under the “other” option to appropriate pre-specified categories. We will use a threshold of <math>\geq 75\%</math> reporting that they were at least somewhat satisfied with the full PrEP2-BAY intervention.
 
After analysis of the quantitative results, we will explore mechanisms of acceptability using a sequential explanatory mixed methods approach. Qualitative interviews from the participants and providers will be performed, a debrief report will be prepared, and audio recordings will be professionally transcribed. Coding and analysis will be performed in the Dedoose cloud-based analysis platform to facilitate collaboration and comparison of coding transcripts. At least 10% of transcripts will be double-coded and compared among the analytic team and inter-coder agreement will be calculated. Inconsistent results will be reviewed by coders until consensus on codes and themes is reached.
 
Preliminary impact on adherence as assessed by hair tenofovir levels (long-term adherence): The first adherence analysis will include use of a mixed effects logistic regression model to estimate the effect of the intervention vs. SoC arm on optimal vs. sub-optimal adherence (<math>< 700</math> fmol/punch) equivalent to at least 4-times weekly average dosing over the prior three months. We will include a random intercept term to account for within-person correlation over two timepoints; and time points will be included as a categorical variable to account for systematic changes over time. We will also analyze continuous tenofovir-diphosphate levels between intervention and SoC arms using a censored-mixed effects linear regression with logarithmically transformed levels of tenofovir in hair.

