#### 3.2 Secondary Objectives

The secondary objective is to assess the impact of the PrEP2-BAY intervention on long-term PrEP adherence (using tenofovir levels in hair) over a three-month period.

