## 10.2 Statistical Analysis

Acceptability, the primary outcome, will be assessed through tabulation of survey results and in-depth interviews. We will use a threshold of  $\geq 75\%$  reporting that the full PrEP-BAY intervention was at least somewhat acceptable on a 5-point Likert scale, and then explore potential mechanisms through in-depth interviews using a sequential explanatory mixed methods approach. For the interviews, we will analyze transcripts using the codebook and theoretical model developed in Aim 2, applying it to a subset of transcripts. We will seek 90% agreement among coders prior to applying codes to the entire set of interviews. We will use code reports to organize findings into emergent themes and discuss these as a group and with the HIV prevention community advisory group.

Preliminary impact (adherence) will be assessed via a long-term adherence metric, namely DBS TFV-DP levels. We will use mixed effects logistic regression for high adherence (at least 4 times weekly dosing; TFV-DP  $\geq 700$  fmol/punch) comparing the interaction of adherence by intervention arm with time. Random intercepts will accommodate paired adherence levels. As an additional adherence outcome, we will examine continuous DBS TFV-DP levels using censored mixed-effects linear regression in a similar fashion.

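### The secondary endpoint is change in hair tenofovir, but both analysis texts lead with a dichotomised outcome, none is named as the main analysis, and section 10.2 specifies a specimen that is not collected

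*Combined protocol and SAP*

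**What the plan says.** **Endpoint.** The synopsis lists under secondary endpoints "Change in tenofovir levels in hair from baseline and after 3 months of follow-up". Section 5.2 says the same and makes it a between-arm comparison: "Change in tenofovir levels in hair from baseline and after 3 months of follow-up will be compared between the intervention" and standard-of-care arms. Neither place mentions a yes/no outcome.

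**Analysis, synopsis (statistics row).** "The first adherence analysis will include use of a mixed effects logistic regression model to estimate the effect of the intervention vs. SoC arm", with adherence classed as optimal or sub-optimal at 700 fmol/punch. Then: "We will also analyze continuous tenofovir-diphosphate levels between intervention and SoC arms". That second sentence names tenofovir-diphosphate but ends by saying that the modelled values are log-transformed hair tenofovir.

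**Analysis, section 10.2.** A mixed logistic model for high adherence comes first, with the same 700 fmol/punch cut-off and an arm-by-time interaction. Then: "As an additional adherence outcome, we will examine continuous". The next words name tenofovir-diphosphate in dried blood spots (DBS), not hair.

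**Specimens.** Sections 9.2 and 12 provide for mailed hair samples, and section 9.3 for urine in the intervention arm only. No blood spot collection is described, and no hair cut-off is given.

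**Status of the objective.** The synopsis primary objective reads "To test the acceptability to participants and impact on a longer-term metric of adherence among participants", so it includes adherence. Section 3.1 limits the primary objective to acceptability, and section 3.2 states: "The secondary objective is to assess the impact of the PrEP2-BAY intervention on long-term PrEP adherence".

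**The concern.** The primary outcome, acceptability, is tabulated in the intervention arm only (section 5.1). Adherence is therefore the only planned outcome compared between randomised arms, and the synopsis says the findings will lead to an application for a larger trial.

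For that comparison the endpoint sections point to a continuous change, while the analysis sections put a dichotomised outcome in front. Dichotomising a continuous level in 40 v 20 people discards information. The two analyses can also disagree, for example with a clear shift in level but few people crossing the cut-off. With no main analysis named, the result to be headlined could then be chosen with the data in hand.

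**Working it through.** **1. Is the order a conflict?**

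| Place | What comes first | What comes second |
|---|---|---|
| Synopsis, secondary endpoints; 5.2 | Change in hair tenofovir (continuous) | nothing |
| Synopsis, statistics row | Binary, 700 fmol/punch | Continuous, log hair tenofovir (also called tenofovir-diphosphate) |
| 10.2 | Binary, DBS tenofovir-diphosphate, 700 fmol/punch | Continuous DBS tenofovir-diphosphate |

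The defined endpoint comes second in the synopsis plan. In 10.2, read literally, it is not analysed at all. The binary outcome, as written, cannot be computed from the specimens collected.

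**2. Is there a power figure to reproduce?** Not for adherence. The only one stated (82%) is for single-arm acceptability. No alpha, effect size, SD, correlation or proportion above the cut-off is given for the adherence comparison.

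**3. Inputs.** From the documents: 40 v 20, two time points, arm-by-time test (10.2). Assumed: two-sided 0.05; normal log hair level with SD 1; effect 0.6 or 0.8 SD; baseline to month 3 correlation ρ of 0.5 or 0.7; 30, 50, 70 or 80% of controls above a hair cut-off; complete and uncensored data. The only background figure is 66-78% with low adherence (section 1), which leaves 22-34% adherent. Participants here are current daily users, so the proportion may be higher.

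**4. Continuous change.** SD of change = √(2(1−ρ)). SE = SD of change × √(1/40 + 1/20) = SD of change × 0.274. Power = Φ(effect/SE − 1.96).

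- Effect 0.6, ρ 0.5: SE 0.274; 0.6/SE = 2.19; power 59%.
- Effect 0.6, ρ 0.7: SE 0.212; 0.6/SE = 2.83; power 81%.
- Effect 0.8, ρ 0.5: SE 0.274; 0.8/SE = 2.92; power 83%.
- Effect 0.8, ρ 0.7: SE 0.212; 0.8/SE = 3.77; power 96%.

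**5. The same data dichotomised.** Random-intercept logistic model, likelihood-ratio test of arm-by-time, 250 simulated trials per cell (about ±6 points):

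| Effect, ρ | Continuous, simulated | Binary at 30 / 50 / 70 / 80% of controls above cut-off | Binary ÷ formula power |
|---|---|---|---|
| 0.6, 0.5 | 54-62% | 28 / 38 / 33 / 21% | 0.36-0.64 |
| 0.6, 0.7 | 75-83% | 35 / 40 / 34 / 29% | 0.36-0.49 |
| 0.8, 0.5 | 80-85% | 54 / 49 / 47 / 38% | 0.46-0.65 |
| 0.8, 0.7 | 96-97% | 61 / 56 / 46 / 45% | 0.47-0.64 |

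Two further simulations of the arm-by-time test gave ratios of 0.34-0.64 (200 runs per scenario, 30-80% above the cut-off) and 0.38-0.67 (400 runs per scenario, 22-70% above).

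**6. A milder comparison, month 3 only.** Take the effect at which the continuous comparison has 80% power: (1.960 + 0.842) × 0.274 = 0.767 SD. If p₁ is the control proportion above the cut-off, the intervention proportion is p₂ = Φ(Φ⁻¹(p₁) + 0.767). For p₁ = 0.70, p₂ = 0.902. With pooled SE 0.102 under no difference and SE 0.113 under the alternative, power = Φ((0.202 − 1.96 × 0.102)/0.113) ≈ 51%. For p₁ of 22, 34, 50, 60, 70, 80 and 90%, power is 55, 59, 59, 56, 51, 43 and 32%. Against 80%, the ratio runs from 0.40 to 0.74. The loss is smaller here, but this is neither the defined endpoint nor the 10.2 test.

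**The case against.** **The continuous analysis is still planned.** This stands. A reader might infer that the plan halves the power of its only randomised comparison. The documents do not support that: both analysis texts include a continuous between-arm model, whose power is unaffected by what is listed before it. The word first in the synopsis can also be read as order of description, since no hierarchy or alpha split is stated. What remains is that nothing says which result answers the secondary objective.

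**The documents do not disagree about the endpoint.** This stands too. A reader might infer that they give opposite answers about whether the endpoint is binary or continuous, but no section calls the binary outcome the endpoint. The conflict lies in the order of the analyses and in the specimen named.

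**The specimen mismatch comes first.** Largely right. Because 10.2 is written in DBS units throughout, the power comparison applies to a dichotomised hair outcome that has yet to be specified. Correcting the specimen would not settle which analysis leads, so both repairs are needed in the same sentences.

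**The size is assumed, and this is a pilot.** Correct. The sample size rests on acceptability, adherence is described as preliminary impact, and no power target is set for it. The simulations ignore dropout, unreturned hair samples and censoring, although a censored model is planned. They also use the 10.2 interaction, whereas the synopsis describes an arm effect with time as a categorical term. A threshold of four doses a week is also easier for clinicians to read. These points limit the weight of the power argument but do not supply a main analysis.

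**The objective wording is minor.** Agreed. The synopsis itself lists hair change as secondary and acceptability as the primary outcome; only its primary objective row is out of line.

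**Conclusion.** The point holds as a failure to name the main analysis of the secondary endpoint, with the weaker analysis placed in front and the wrong specimen in 10.2. Under the assumptions listed, a dichotomised arm-by-time test has roughly one-third to two-thirds of the power of the continuous change analysis. About half is a fair mid-range description, but it is not a fixed figure and cannot be derived from the documents.

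The change should be made before outcome data are examined. The primary endpoint and the sample size are unaffected.

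**What to change.** 1. In the synopsis statistics row and in 10.2, name the between-arm difference in change in log hair tenofovir as the main analysis of the secondary endpoint. Use the censored linear mixed model already in the synopsis, with the arm-by-time term stated as the estimate of interest in both places.
2. Replace the tenofovir-diphosphate and DBS wording with hair tenofovir throughout both texts, and remove the fmol/punch cut-off from the hair analysis.
3. Keep a dichotomised result only as supportive, reported as counts by arm and visit with a risk difference and confidence interval, and only if a hair-based cut-off is specified in advance. Otherwise drop it.
4. Align the synopsis primary objective with sections 3.1, 3.2 and 5.2, so that adherence impact is secondary.

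Cost: redrafting a few sentences, with no new specimens, visits or participants. Section 10.2 needs more than reordering, because neither of its analyses currently refers to hair. The downside is that the familiar adequate-adherence contrast becomes supportive.

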## **6 SUBJECT SELECTION**

### **6.1 Study Population**

We will recruit 60 YMSM (ages 18-30), who are male sex at birth, through advertisements on social networks who are currently using PrEP who are willing to give urine and hair biospecimens and to enroll in the PrEP-BAY trial. We will obtain written informed consent from participants prior to enrollment in the study.

### **6.2 Inclusion Criteria**

1. Age 18-30 years.
2. Primary sexual partners are male sex at birth
3. Able to understand, read, and speak English.
4. Currently taking TDF/FTC-based, daily PrEP and planning to continue for at least 3 months
5. Willing to provide a self-collected hair sample

### **6.3 Exclusion Criteria**

1. Any health condition that may interfere with participation or the ability to provide informed consent, including any debilitating or life-threatening conditions
2. Currently enrolled in another HIV intervention study.
3. Known to be HIV-infected

## **7 CONCURRENT MEDICATIONS**

The participant may continue to use concomitant medications as recommended by the primary PrEP provider. The study will not provide PrEP medication and will not review PrEP safety labs. The study will provide additional PrEP adherence counseling only in the intervention arm, and the standard of care arm will receive no changes to the current PrEP care that they are receiving outside of the study. Concomitant medications will not be collected as they are not expected to impact interpretation of study results.

## **8 RANDOMIZATION**

### **8.1 Method of Assigning Subjects to Treatment Groups**

Up to 60 eligible participants will be randomly assigned to the PrEP-BAY adherence counseling intervention or to continue standard of care with study assessments only in a 2:1 ratio using a Stata-based computer-generated randomization scheme developed by the study statistician, which will be integrated into the Redcap study tracking forms.

### **8.2 Blinding**

Due to the intervention involving an adherence counseling intervention, all procedures will be open-label and no blinding will occur.

## 9 STUDY PROCEDURES AND GUIDELINES

### 9.1 Recruitment and Consent:

This study involves two video (Zoom)/phone research visits for each of the 60 participants. Potential participants who are interested in participating in the study will contact the recruitment website/email address provided on recruitment notices on social networks. First, the study coordinator(s) will evaluate participants for eligibility for the study as per the inclusion criteria above. All participants will be informed of the purpose of the study, risks and discomforts involved, potential benefits, etc. Participants will be given as much time as necessary to consider study participation and are offered the opportunity to review the consent form on their own to provide adequate time to consider participation. The study team will engage the potential participant in a dialogue, using open-ended questions about the nature of the study or the experimental treatment, the risks and benefits of participating, and the voluntary nature of participation. Potential participants will be asked or shown a series of questions to assess their understanding of the study purpose, procedures, risks and benefits, as well as the voluntary nature of participation. Informed consent will occur remotely using the phone/zoom, and the signature via Docusign.

### Randomization

Randomization will occur in the screening/enrollment visit after the informed consent procedures are performed. Eligible participants will be randomly assigned to the PrEP2-BAY adherence counseling intervention or to continue standard of care with study assessments only in a 2:1 ratio using a Stata-based computer-generated randomization scheme.

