### 9.2 Hair Sample Collection

Prior to the Month 0 visit, hair collection instructions will be sent to the participant. Instructions will be provided and will be reviewed with the participant at the Month 0 visit. All participants will self-collect (at home) hair samples using a pair of scissors at study enrollment and at three months and will place them in a pre-addressed and prepaid envelope to be sent back to the UCSF HAL. Approximately 50 strands of hair will be collected (less than is lost from the scalp in a day). Home collected hair specimens will be used for measurement of tenofovir, a marker of long-term adherence to PrEP. Participants will send the hair sample via the mail to the UCSF Hair Analytic Lab for analysis. No other analyses will be performed on this sample and it will be destroyed after analysis.

	Screening/ Enrollment	Month 0	Month 3
Assess eligibility	√		
Informed consent	√		
Randomization	√		

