### 9.3 Urine Sample Collection and Analysis (Intervention Arm Only)

Prior to the Month 0 visit, urine test kits will be sent to all participants in the intervention arm. Urine samples will be collected by the participant before or during the video visit only for participants in the intervention arm. Urine is collected with a volume of at least 5mL into a

urine collection cup provided to the participant. The urine may be collected at the beginning of the urine stream (no need for clean catch). The participant will be provided instructions on how to complete the urine test, and may discuss any questions with the research coordinator at the time of enrollment/first study visit

The participant will be provided a \$50 cash or gift card reimbursement for completion of all study procedures at each visit, including the survey and urine collection. Reimbursement may be provided via an e-gift card or check.

Hair TFV Levels		√	√
POC Urine Testing (intervention arm only)		√	√
PrEP2-BAY Counseling Intervention (intervention arm only)		√	√
Online questionnaire		√	√

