#### **9.5 Survey Collection**

The quantitative survey will be performed and collected using Redcap software either on the participants phone or home computer. The participant identification number will be inputted into the survey to allow linking of the survey to the participant's urine sample. The survey will take 20-30 minutes to complete and contains approximately 100 questions. The survey will be completed by the participant after each research visit.

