## **12. Laboratory Specimens and Biohazard Containment**

Hair specimens will be collected at screening and at the month 3. Specimens will be collected via home mailer and shipped to the UCSF Hair Analytical Laboratory. There is no risk of bloodborne pathogen transmission via hair samples.

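### Baseline hair is scheduled after open-label allocation and its timing is stated inconsistently; the Month 0 survey is not a pre-treatment measure in the intervention arm

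*Combined protocol and SAP*

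**What the plan says.** Allocation comes early and is known. The Randomization text in Section 9.1 says "Randomization will occur in the screening/enrollment visit after the informed consent procedures are performed", and Section 8.2 says "all procedures will be open-label and no blinding will occur". The synopsis plans "60 participants, 40 in the intervention arm and 20 in the standard-of-care arm".

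The timing of the first hair sample is given in three places:

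- **Schedule table (split across Sections 9.2 and 9.3).** The row "Hair TFV Levels" is ticked at Month 0 and Month 3. Its screening/enrollment cell is blank, while randomisation is ticked there.
- **Section 9.2.** Hair is self-cut at home at enrollment and at three months, then mailed. Instructions are sent before Month 0, and the section adds: "Instructions will be provided and will be reviewed with the participant at the Month 0 visit".
- **Section 12.** "Hair specimens will be collected at screening and at the month 3".

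Section 9.3 says: "Prior to the Month 0 visit, urine test kits will be sent to all participants in the intervention arm". The table places urine testing and counseling, both for the intervention arm only, at Month 0 and Month 3. Section 9.4 says the sessions discuss the urine result.

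On the questionnaire, Section 9.5 says "The survey will be completed by the participant after each research visit". The table shows no questionnaire before Month 0.

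Section 5.2 defines the secondary endpoint as the change in hair tenofovir from baseline to three months, compared between arms.

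**The concern.** A baseline is most useful in a randomised comparison when it is obtained before anyone knows the arm. Here the participant cuts and mails the sample, and by the schedule already knows the allocation. A person assigned to continue usual care may have less reason to send hair promptly, or at all, than one who has received a test kit and expects counseling. If return or its timing differs by arm for reasons linked to adherence, the two arms' baseline samples no longer represent the groups that were randomised. The secondary hair endpoint rests on that comparison, and the synopsis says the findings will lead to an application for a multi-city trial, which may inherit the same ordering.

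A second, separate matter is the Month 0 questionnaire. Its place in the schedule suggests a baseline measure, but in one arm it is answered after urine feedback and the first counseling session.

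**Working it through.** No sample-size, power or alpha figure bears on this point, so there is no figure of the plan's to reproduce. The check is mainly one of sequence.

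**1. Does allocation precede Month 0?** Yes. Section 9.1 mentions two research visits per participant, so enrollment and Month 0 might be read as one contact. But the kits go to one arm only and must be sent before Month 0. That requires allocation to exist beforehand, with time for delivery. Receiving a kit, or not, also reveals the arm.

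**2. Does baseline hair precede allocation?**

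| Source | First hair sample | Relative to randomisation |
|---|---|---|
| Schedule table | Month 0 | After |
| Section 9.2 | Enrollment, instructions reviewed at Month 0 | Not stated; the review at Month 0 points to after |
| Section 12 | Screening | Same visit as randomisation, order not stated |

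Section 13.3 requires consent before any study procedure, and randomisation follows consent in the same visit. Under Section 12, hair could come before allocation only if it were cut between those two steps. Nothing requires that order.

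**3. Does baseline hair precede session 1?** Not determined. Instructions arrive before Month 0 and are reviewed at it, so the hair could be cut before, during or after that visit. No cutting date is required.

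**4. How far could a delay move the hair level?** The documents give neither the gap from allocation to cutting nor the length of the hair window. Assume a 13-week window (about three months):

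share of window after allocation = gap in weeks / 13

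| Gap (weeks, assumed) | Share |
|---|---|
| 0 | 0/13 = 0% |
| 1 | 1/13 = 8% |
| 2 | 2/13 = 15% |
| 4 | 4/13 = 31% |

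If the level averages evenly over the window, only that share of any early change in pill-taking enters the baseline. A short gap therefore matters little; an uncontrolled gap of a month would matter more.

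**5. What does non-return do?** With the planned numbers, each missing baseline sample is 1/20 = 5% of the control arm or 1/40 = 2.5% of the intervention arm. The documents give no expected return rate and nothing on how return relates to adherence, so a bias cannot be computed.

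**6. Survey order at Month 0.** Intervention arm: urine test, session 1, survey. Control arm: visit without either, survey. As planned, all 40 intervention participants give their first self-report after treatment has begun, and none of the 20 controls do. This describes the design; it is not a bias estimate, because no planned between-arm analysis uses the survey.

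**The case against.** The strongest reply is that little in the planned analysis is harmed, and much of it stands.

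- **Treatment effect on the hair baseline.** A reader might infer that counseling contaminates it. The documents do not say that hair is cut after session 1, and Sections 9.2 and 12 suggest earlier collection. The marker is also cumulative. What remains is that nothing prevents late cutting.
- **Loss of participants.** A reader might infer that anyone who fails to return baseline hair drops out of the analysis. The synopsis and Section 10.2 specify mixed models with a random intercept, which keep a person with a single sample, and nothing restricts the analysis to complete pairs. But such a model does not correct non-return that depends on the arm and on the level that was not observed.
- **Stable differences cancel.** If non-returners have lower levels by the same amount at both times and are absent from both, a change score is unaffected. Bias needs return to be related to change, or to be missing in a pattern the model cannot recover.
- **Safeguards.** Willingness to give self-collected hair is an inclusion criterion (Section 6.2), envelopes are prepaid (Section 9.2), and the payment for completing each visit's procedures is not limited to one arm (Section 9.3). These reduce arm-dependent return without excluding it.
- **Survey timing.** A reader might infer that it distorts the change endpoint. It does not: that endpoint is hair only, and the models list no survey covariate. Acceptability is assessed in the intervention arm and has to be asked after exposure. Nor is interview selection biased between arms, since Section 9.6 samples from the intervention arm alone and does not name the Month 0 survey as the source of reported adherence challenges.

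**Conclusion.** The point holds in a limited form. The statements on baseline hair timing conflict and must be reconciled. Under the schedule as drawn, baseline hair is obtained after participants know their arm, so its return and timing can depend on the arm. That is the main risk, and it falls on the secondary hair endpoint. A shift in the level from delay alone is small if the gap is short: about 8% of the window for one week, under the assumed 13 weeks and even averaging. The size of any bias from arm-dependent return is unknown, because the documents give no return rates.

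Separately, the Month 0 questionnaire cannot serve as a pre-treatment measure in the intervention arm. No planned analysis relies on it as one, so the loss is of descriptive baseline data and of possible later use as covariates.

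The acceptability primary is unaffected. This is a cheap improvement to a pilot and not a defect that undermines it.

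**What to change.** Revise Sections 9.1, 9.2, 9.5 and 12 and the schedule table so that they give one order:

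1. Obtain consent.
2. Review the hair instructions. All participants then cut and post the baseline hair, with the cutting date recorded, and complete the baseline questionnaire items.
3. Release the allocation in REDCap, where Section 8.1 already places the randomisation scheme, once both items are marked complete. Marking hair complete only when posted, not merely cut, also protects its return from knowledge of the arm.
4. Send urine kits to the intervention arm, then hold the Month 0 visit with session 1.
5. Keep only the satisfaction items in the post-session survey.

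If disclosure cannot wait, the minimum is that hair and baseline items are complete before session 1, with the cutting date recorded. In either case, report baseline hair return and cutting dates by arm.

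The cost is a short delay between consent and randomisation and a questionnaire split in two. Some people who consent may not send hair and so would not be randomised. No new procedure or specimen is needed.
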